5.3.1 Adverse Event Reporting Period

Investigators will seek information on adverse events at each patient contact. All adverse events, whether reported by the patient or noted by study personnel, will be recorded in the patient's medical record and on the Adverse Event eCRF.

After informed consent has been obtained **but prior to initiation of study drug**, only serious adverse events caused by a protocol-mandated intervention (e.g., invasive

procedures such as biopsies, discontinuation of medications) should be reported (see Section 5.4.2 for instructions for reporting serious adverse events).

After initiation of study drug, all adverse events, serious adverse events, and adverse events of special interest will be reported until 135 days after the last dose of study drug, or until a new systemic anti-cancer therapy is initiated, whichever occurs first.

Instructions for reporting adverse events that occur after the adverse event reporting period are provided in Section 5.6.

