5.6 ADVERSE EVENTS THAT OCCUR AFTER THE ADVERSE EVENT REPORTING PERIOD

After the end of the adverse event reporting period (defined as 135 days for all adverse events, serious adverse events, and adverse events of special interest after the last dose of study drug, or until a new systemic anti-cancer therapy is initiated, whichever occurs first), all deaths, regardless of cause, should be reported through use of the Long-Term Survival Follow-Up eCRF or Post-Study Reporting of Death by Public Records eCRF, as appropriate. If the patient withdraws from the study, the study staff may use a public information source (e.g., county records) to obtain information about survival status only. In addition, if the investigator becomes aware of a serious adverse event that is believed to be related to prior study drug treatment, the event should be reported through use of the Adverse Event eCRF. However, if the EDC system is not available, the investigator should report these events directly to the Sponsor or its designee, either by faxing or by scanning and emailing the paper Clinical Trial Serious

Adverse Event/Adverse Event of Special Interest Reporting Form using the fax number or email address provided to investigators.

5.7 EXPEDITED REPORTING TO HEALTH AUTHORITIES, INVESTIGATORS, INSTITUTIONAL REVIEW BOARDS, AND ETHICS COMMITTEES

The Sponsor will promptly evaluate all serious adverse events and adverse events of special interest against cumulative product experience to identify and expeditiously communicate possible new safety findings to investigators, IRBs, ECs, and applicable health authorities based on applicable legislation.

To determine reporting requirements for single adverse event cases, the Sponsor will assess the expectedness of these events using the following reference documents:

- Cobimetinib Investigator's Brochure
- Atezolizumab Investigator's Brochure
- Local prescribing information for pembrolizumab

The Sponsor will compare the severity of each event and the cumulative event frequency reported for the study with the severity and frequency reported in the applicable reference document.

Reporting requirements will also be based on the investigator's assessment of causality and seriousness, with allowance for upgrading by the Sponsor as needed.

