2.2.5 Safety Endpoints

- Occurrence and severity of AEs, with severity determined through use of NCI CTCAE v4.0
- Change from baseline in selected vital signs
- Change from baseline in selected clinical laboratory test results

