2.3 DETERMINATION OF SAMPLE SIZE

Approximately 450 patients will be randomized into the study.

The overall type I error (α) for this study is 0.05 (two-sided). Formal treatment comparisons will be performed by first evaluating the primary endpoint of IRC-assessed PFS (per RECIST v1.1) at $\alpha=0.01$ (two-sided). If PFS is statistically significant at $\alpha=0.01$, then the key secondary endpoints will be evaluated at $\alpha=0.05$ (two-sided) in a hierarchical manner in the following order: OS, IRC-assessed objective response rate (ORR), and landmark OS. IRC-assessed ORR and landmark OS will be tested when OS crosses the pre-specified boundary.

The type I error (α) for the analysis of the primary endpoint of IRC-assessed PFS is 0.01 (two-sided). The analysis of the primary endpoint of IRC-assessed PFS will take place when approximately 240 PFS events have occurred. Statistical considerations are based on the following assumptions:

- Stratified log-rank test at 0.01 significance level (two-sided)
- Median PFS of 5.5 months for the pembrolizumab arm
- Median PFS of 10.0 months for the cobimetinib plus atezolizumab arm
- Enrollment period of approximately 12 months
- Annual dropout rate of 5%
- No interim analysis for PFS

A total of 240 PFS events provides approximately 98% power to detect an improvement in median PFS from 5.5 months in the pembrolizumab arm to 10.0 months in the cobimetinib plus atezolizumab arm. This corresponds to a hazard ratio (HR) of 0.55, with a minimal detectable difference of 0.72. The PFS analysis will be conducted approximately 17 months after first patient in (FPI). The final analysis of the secondary endpoint of OS will be performed after the occurrence of approximately 295 deaths. A total of 295 deaths provides approximately 60% power to detect an improvement in median OS from 28 months in the pembrolizumab arm to 37.5 months in the cobimetinib plus atezolizumab arm, corresponding to an HR of 0.75, or 80% power to detect an HR of 0.70. Two interim analyses of OS will be conducted. The final OS analysis will be conducted approximately 68 months after FPI.

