4.5.1 Exposure of Study Medication

Study drug exposure, including treatment duration, number of cycles, and dose intensity, will be summarized for each treatment arm with descriptive statistics.

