4.5.2 Adverse Events

Verbatim description of AEs will be summarized by mapped terms and appropriate thesaurus levels and graded according to NCI CTCAE v4.0. All AEs that occur during or after the first study drug dose will be summarized by treatment arm and NCI CTCAE grade. In addition, serious adverse events (SAEs), severe AEs (Grade ≥ 3), adverse events of special interest (AESI), and AEs leading to study drug discontinuation or interruption will be summarized accordingly. Multiple occurrences of the same event will be counted once at the maximum severity. The proportion of patients who experience at least one AE event will be reported by toxicity term and treatment arm.

All deaths and causes of death will be summarized by treatment arm.

Listings of AEs will include all AEs with an onset that occurred on or after the first study drug treatment up to the data cutoff date.

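### Adverse events are summarised by arm only as crude proportions over a collection window that follows time on drug, so any difference in treatment duration confounds the comparison, in either direction

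*SAP*

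**What the plan says.** The safety objective is comparative: Protocol Section 2, Table 1 sets out to evaluate the safety of the combination against pembrolizumab. The first endpoint for it is "Occurrence and severity of AEs, with severity determined through use of NCI CTCAE v4.0" (SAP 2.2.5).

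Collection of all adverse events runs "until 135 days after the last dose of study drug, or until a new systemic anti-cancer therapy is initiated, whichever occurs first" (Protocol 5.3.1). After that, Protocol 5.6 still asks for all deaths, and for a report "if the investigator becomes aware of a serious adverse event that is believed to be related to prior study drug treatment". Treatment itself runs to confirmed investigator-assessed progression, unacceptable toxicity, withdrawal or another listed reason, with the same rule in both arms (SAP Section 2).

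The planned summary is "The proportion of patients who experience at least one AE event will be reported by toxicity term and treatment arm" (SAP 4.5.2; Protocol 6.5 is equivalent), under the counting rule "Multiple occurrences of the same event will be counted once at the maximum severity". Time on drug has its own section: "Study drug exposure, including treatment duration, number of cycles, and dose intensity, will be summarized for each treatment arm with descriptive statistics" (SAP 4.5.1). Neither document uses that duration as a denominator for adverse events. Neither plans a rate per patient-time, a time-to-first-event or cumulative incidence display, or a fixed common window.

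**The concern.** A crude proportion of patients with at least one event depends on two things: how often events occur, and how long each patient is watched for them. Here the second is tied to the last dose, which depends mainly on progression and tolerability. If the arms differ in time on drug, the difference in proportions mixes toxicity with observation time. Equal event rates would look like an excess in the arm treated longer. If the combination were stopped earlier, a real excess of toxicity would be understated.

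The design gives a reason to expect unequal durations. It assumes "Median PFS of 10.0 months for the cobimetinib plus atezolizumab arm" against 5.5 months for pembrolizumab, with treatment to progression. What is at stake is how readers interpret the side-by-side percentages, since these are the only between-arm adverse event comparison the plan produces.

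**Working it through.** **The plan's own figure.** The safety sections state no number, so the design figure behind the expected difference was checked. With 240 events, HR 0.55 and two-sided α = 0.01, power = Φ(√240/2 × |ln 0.55| − 2.576) = Φ(4.631 − 2.576) = Φ(2.055) = 98.0%. The SAP states about 98%.

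**Inputs from the documents.** PFS medians 10.0 and 5.5 months, 12-month enrolment and cutoff at month 17 (SAP 2.3); window of 135 days = 135/30.4375 = 4.44 months (Protocol 5.3.1).

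**Assumptions, not in the documents.** Time on drug equals the planning PFS and is exponential; accrual is uniform, so follow-up u runs from 5 to 17 months; the adverse event hazard h is constant and identical in both arms; no dropout.

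**Formulas.** Let λ = ln 2/median, giving 0.0693 (A) and 0.1260 (B), let k = h + λ, and let W = 4.44. Let M(a, b) be the mean of e^(−ku) for u uniform on (a, b), that is (e^(−ka) − e^(−kb))/(k(b − a)).

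- New therapy starts at once, so the window ends with treatment: P = (h/k) × [1 − M(5, 17)].
- Full 135 days: P = 1 − e^(−hW) + e^(−hW) × (h/k) × [1 − M(5 − W, 17 − W)].

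**Worked case, h = 0.05.**
- At once, A: (0.05/0.1193) × (1 − 0.2927) = 29.6%. B: (0.05/0.1760) × (1 − 0.1726) = 23.5%.
- Full window, A: 0.1989 + 0.8011 × 0.4191 × (1 − 0.4970) = 36.8%. B: 0.1989 + 0.8011 × 0.2840 × (1 − 0.3768) = 34.1%.

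| h per month | New therapy at once, A vs B | Gap (points) | Full 135 days, A vs B | Gap (points) |
|---|---|---|---|---|
| 0.02 | 13.6% vs 10.6% | 3.0 | 17.0% vs 15.6% | 1.4 |
| 0.05 | 29.6% vs 23.5% | 6.1 | 36.8% vs 34.1% | 2.7 |
| 0.10 | 48.2% vs 39.3% | 8.9 | 59.0% vs 55.6% | 3.4 |

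Mean treatment time under these inputs is 7.5 vs 5.8 months. First events per patient-time at risk would be h in both arms, a ratio of 1.00.

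**Sensitivity (simulation, 1,000,000 patients per arm, with the plan's 5% annual dropout added).**
- Month-17 cutoff: mean observation time in A vs B is 9.2 vs 8.4 months with the full window, and 7.3 vs 5.7 if new therapy starts at once.
- No cutoff, collection complete: a 20% control proportion corresponds to 27.2% in Arm A with the full window and 30.7% with immediate new therapy.
- Events arising only in the first 3 months: no gap with the full window. With immediate new therapy the gap is 1.6 points at a 20% control proportion and 4.0 at 60%.
- Equal PFS in both arms: 8.38 vs 8.39 months, no gap.
- An extra Arm A toxicity-stop hazard of about 0.057 per month: 8.39 vs 8.38 months, no gap. At 0.08 per month Arm A is observed for less time (8.10 vs 8.39) and the distortion reverses.

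**The case against.** The strongest reply is that the plan favours neither arm. Stopping and collection rules are common to both, and the windows diverge only if time on drug does. A reader might infer that Arm A must show more events by construction, or that a gap of the size above is present in the final data. The documents support neither. No treatment duration is planned. IRC-assessed PFS is not time on drug, because dosing follows investigator-assessed confirmed progression, may continue beyond progression, and ends early for toxicity. SAP 2.5 records that no benefit was demonstrated, so the planning medians cannot be carried into the final data. This all stands, and it limits the point to confounding of unknown direction. It does not remove it: toxicity stops can also separate the windows, and in Arm A a patient who stops one drug may continue the other (Protocol 4.6.2).

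A reader might also infer that nothing is collected after the window. That is wrong: deaths and serious events believed related are still reported. Other Grade 3 or higher and special-interest events remain bound by the window.

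It is fair, too, that no safety hypothesis is tested, that SAP 4.5.1 would reveal an imbalance in duration, and that the crude proportion validly describes absolute risk under each treatment strategy. That is why the crude tables should stay. But showing an imbalance does not adjust for it, and a reader cannot make the adjustment from separate summaries.

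**Conclusion.** The point holds as a gap in the analysis plan. Adverse events are summarised only as crude proportions, the window follows time on drug, and nothing planned separates event frequency from length of observation. Under the planning medians and an identical constant hazard of 0.02 to 0.10 per month, the crude comparison at month 17 would favour pembrolizumab by about 1.4 to 3.4 points with the full 135 days, and by 3.0 to 8.9 points if every patient began new therapy the day treatment stopped. The upper end needs that extreme assumption. These sizes illustrate sensitivity and are not estimates for this trial. Correcting the gap is a cheap improvement; it does not invalidate the planned tables.

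**What to change.** In SAP 4.5.2, keep the crude tables and add, for Grade 3 or higher, serious and special-interest adverse events:

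- **Rates:** first events per 100 patient-years of adverse event reporting window, by arm, with 95% CIs.
- **Cumulative incidence:** first event at 6 and 12 months (Aalen-Johansen), with death before the event as a competing event and the administrative data cutoff as censoring. Treat the end of the reporting window (135 days or new therapy) as a competing event in the main display and as censoring in a sensitivity display. Both are needed: the first still depends on window length, and the second can be informative when toxicity caused the stop.

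Present these as supplementary, label them as specified after the primary result, and interpret the crude differences alongside them.

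Also reconcile Protocol 5.4.2.2, which refers to serious events more than 90 days after the last dose as falling under Section 5.6, with the 135 days in Sections 5.3.1 and 5.6. That window defines the denominator.

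The cost is SAP wording and a few extra tables from dates already collected. The rates assume a roughly constant hazard; the cumulative incidence display covers that weakness.

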4.5.3 Laboratory Data

Laboratory data will be summarized over time including change from baseline by treatment arm. Values outside the normal ranges will be summarized. Additionally, selected laboratory data will be classified in accordance with NCI CTCAE v4.0 and will be summarized by grade and treatment arm. Highest NCI CTCAE grade post-baseline will also be reported, and shift tables from baseline to worst value during the study post-baseline will be presented.

4.5.4 Vital Signs

Changes in selected vital signs will be summarized by treatment arm and by change over time including change from baseline.

4.6 PHARMACOKINETIC AND PHARMACODYNAMIC ANALYSES

The PK analyses will include patients who have received at least one dose of study drug and for whom at least one evaluable PK sample is collected (actual dose and actual sampling time recorded for each sample). Because only a few samples will be collected from patients, data will be analyzed using existing population PK models for post-hoc estimates of apparent clearance or systemic clearance for cobimetinib and atezolizumab, respectively. The maximum or minimum concentration (C_{\max} or C_{\min}) will be reported for individual patients and summarized by study day, as the data permit. [REDACTED]

Additional PK analyses will be conducted as appropriate based on the available data.

4.7 IMMUNOGENICITY ANALYSES

The immunogenicity analyses for atezolizumab will include patients from Arm A with any ADA assessment. The numbers and proportion of ADA-positive patients and ADA-negative patients at baseline (baseline prevalence) and after baseline (post-baseline incidence) will be summarized by disease status (metastatic or locally advanced and unresectable). When determining the post-baseline incidence, patients are considered to be ADA positive if they are ADA negative or have missing data at baseline but develop an ADA response following study drug exposure (treatment-induced ADA response), or if they are ADA positive at baseline and the titer of one or more post-baseline samples is at least 0.60-titer unit greater than the titer of the baseline sample (treatment-enhanced ADA response). Patients are considered to be ADA negative if they are ADA negative or have missing data at baseline and all post-baseline samples are negative, or if they are ADA positive at baseline but do not have any post-baseline samples with a titer that is at least 0.60-titer unit greater than the titer of the baseline sample (treatment unaffected).

The relationship between ADA status and safety, efficacy, pharmacokinetics, and biomarker endpoints may be analyzed and reported using descriptive statistics.

4.8 BIOMARKER ANALYSES

Efficacy will be explored in biomarker subgroups defined by PD-L1 expression, CD8 T-cell density, tumor mutation burden based on next-generation sequencing, and other significant biomarkers at the conclusion of this study.

NGS data will also be analyzed in the context of this study and explored in aggregate with data from other studies to increase researchers' understanding of disease pathobiology and guide the development of new therapeutic approaches.

4.9 MISSING DATA

Please refer to Sections 4.4.1 and 4.4.2 for methods of handling missing data for the primary and secondary efficacy endpoints.

4.10 INTERIM ANALYSES

No interim analyses are planned for PFS.

The study will incorporate three OS analyses (two interim analyses and one final analysis).

Table 1 summarizes the assumptions and characteristics of the interim and final analyses for OS. The actual number of observed OS events at each interim analysis may differ from the estimates presented. The stopping boundaries are computed using Generalized Haybittle-Peto boundaries with unequal p-values of 0.001, 0.040, and 0.018 at the three OS analyses to control the overall type I error of the OS comparison at a two-sided 0.05 significance level.

Given that the study did not meet the primary endpoint, the second interim and final OS analysis will not be conducted as specified above. Instead, a final OS analysis will be conducted at the time of final database lock.

Table 1 Assumptions and Characteristics for the Interim and Final Analyses of Overall Survival

Assumptions	Findings
HR targeted	0.75
Targeted median (pembrolizumab)	28.0 months
Targeted median (cobimetinib + atezolizumab)	37.5 months
Projected enrollment period	12 months
First interim analysis (performed at the time of the PFS analysis)	
Estimated cutoff date ^a	17 months
Projected number of events (% of final events)	80 (27%)
Projected MDD ^b (p-value)	0.42 (<0.001)
Second interim analysis	
Estimated cutoff date ^a	28 months
Projected number of events (% of final events)	153 (52%)
Projected MDD ^b (p-value)	0.72 (<0.040)
Final analysis	
Estimated cutoff date ^a	68 months
Projected number of events (% of final events)	295 (100%)
Projected MDD ^b (p-value)	0.76 (<0.018)
Power	60%
α level (two-sided)	0.05

HR=hazard ratio; MDD=minimally detectable difference; PFS=progression-free survival;

^a Estimated data cutoff time from first randomization. Analysis results will be available after data cleaning.

^b The largest observed HR that is projected to be statistically significant.

5. **REFERENCES**

Greenwood M. The natural duration of cancer. *Reports on Public Health and Medical Subjects* 1926;33:1–26. Her Majesty's Stationery Office, London.

Appendix 1 Protocol Synopsis

TITLE: A PHASE III, OPEN-LABEL, MULTICENTER, TWO-ARM, RANDOMIZED STUDY TO INVESTIGATE THE EFFICACY AND SAFETY OF COBIMETINIB PLUS ATEZOLIZUMAB VERSUS PEMBROLIZUMAB IN PATIENTS WITH PREVIOUSLY UNTREATED ADVANCED *BRAF*^{V600} WILD-TYPE MELANOMA

PROTOCOL NUMBER: CO39722

VERSION NUMBER: 5

EUDRACT NUMBER: 2016-004387-18

IND NUMBER: 135,717

TEST PRODUCTS: Cobimetinib (RO5514041)
Atezolizumab (RO5541267)

PHASE: Phase III

INDICATION: Metastatic *BRAF*^{V600} wild-type melanoma

SPONSOR: F. Hoffmann-La Roche Ltd

Objectives and Endpoints

This study will evaluate the efficacy, safety, and pharmacokinetics of cobimetinib plus atezolizumab compared with pembrolizumab in patients with treatment-naive advanced *BRAF*^{V600} wild-type melanoma. Specific objectives and corresponding endpoints for the study are outlined in the following table.

Objectives and Corresponding Endpoints

Objective(s)	Corresponding Endpoint(s)
Primary Efficacy Objective:	

 To evaluate the efficacy of cobimetinib plus atezolizumab compared with pembrolizumab, as measured by the primary endpoint of PFS by independent review 	
 PFS, defined as the time from randomization to the first occurrence of disease progression, as determined by an IRC according to RECIST v1.1, or death from any cause, whichever occurs first

Objectives and Corresponding Endpoints (cont.)

Objective(s)	Corresponding Endpoint(s)
Secondary Efficacy Objectives:	

 • To evaluate the efficacy of cobimetinib plus atezolizumab compared with pembrolizumab, as measured by OS and 2-year landmark OS • To evaluate the efficacy of cobimetinib plus atezolizumab compared with pembrolizumab, as measured by ORR • To evaluate the efficacy of cobimetinib plus atezolizumab compared with pembrolizumab, as measured by investigator-assessed PFS • To evaluate the efficacy of cobimetinib plus atezolizumab compared with pembrolizumab, as measured by DCR • To evaluate the efficacy of cobimetinib plus atezolizumab compared with pembrolizumab, as measured by DOR • To evaluate the efficacy of cobimetinib plus atezolizumab compared with pembrolizumab, as measured by the change from baseline in HRQoL 	
 • OS, defined as the time from randomization to death from any cause • Two-year landmark survival, defined as survival at 2 years • Objective response, defined as a complete response or partial response on two consecutive occasions ≥ 4 weeks apart, as determined by an IRC according to RECIST v1.1 • Objective response, defined as a complete response or a partial response on two consecutive occasions ≥ 4 weeks apart, as determined by the investigator through use of RECIST v1.1 • PFS, defined as the time from randomization to the first occurrence of disease progression, as determined by the investigator through use of RECIST v1.1, or death from any cause, whichever occurs first • DCR, defined as the proportion of patients with a complete response, a partial response, or stable disease at 16 weeks, as determined by the IRC through use of RECIST v1.1 • DCR, defined as the proportion of patients with a complete response, a partial response, or stable disease at 16 weeks, as determined by the investigator through use of RECIST v1.1 • Duration of objective response, defined as the time from the first occurrence of a documented objective response to disease progression, as determined by an IRC through use of RECIST v1.1, or death from any cause, whichever occurs first • Duration of objective response, defined as the time from the first occurrence of a documented objective response to disease progression, as determined by the investigator through use of RECIST v1.1, or death from any cause, whichever occurs first • The change from baseline in HRQoL scores, as assessed through use of the two-item GHS/QOL subscale of the European Organization for Research and Treatment of Cancer Quality of Life Core 30 questionnaire (EORTC QLQ-C30), at specified timepoints while receiving treatment

Objectives and Corresponding Endpoints (cont.)

Objective(s)	Corresponding Endpoint(s)
Exploratory Efficacy Objectives:	

 To evaluate the efficacy of cobimetinib plus atezolizumab compared with pembrolizumab, as measured by the investigator, according to immune-modified RECIST To evaluate the efficacy of cobimetinib plus atezolizumab compared with pembrolizumab, as measured by change from baseline in functioning and commonly reported symptoms 	
 Objective response according to investigator-assessed immune-modified RECIST DOR according to investigator-assessed immune-modified RECIST PFS according to investigator-assessed immune-modified RECIST Change from baseline in HRQoL, functioning and commonly reported symptoms (insomnia, pain, and fatigue), as assessed through use of the EORTC QLQ-C30 GHS, functioning and symptom scales, at specified timepoints, including progression, treatment discontinuation and post-study treatment The number and proportion of patients who improve, remained stable, and worsen from baseline as measured by the EORTC QLQ-C30 GHS, functioning, and symptom scales, at specified timepoints, including progression, treatment discontinuation and post-study treatment
Safety Objective:	

 To evaluate the safety of cobimetinib plus atezolizumab compared with pembrolizumab 	
 Occurrence and severity of adverse events, with severity determined through use of NCI CTCAE v4.0 Change from baseline in selected vital signs Change from baseline in selected clinical laboratory test results
Pharmacokinetic Objective:	

 To characterize the cobimetinib and atezolizumab pharmacokinetics when administered in combination in this patient population 	
 Plasma concentration of cobimetinib at specified timepoints Serum concentration of atezolizumab at specified timepoints
Exploratory Pharmacokinetic Objective:	

	

Objectives and Corresponding Endpoints (cont.)

Objectives	Corresponding Endpoint(s)
Immunogenicity Objective:	

 To evaluate the immune response to atezolizumab 	
 Incidence of ADAs during the study relative to the prevalence of ADAs at baseline
Exploratory Immunogenicity Objective:	

 To evaluate potential effects of ADAs 	
 Relationship between ADA status and efficacy, safety, or PK endpoints
Exploratory Biomarker Objective:	

 To explore biomarkers that are associated with response or resistance to cobimetinib plus atezolizumab 	
 Relationship of immune contextures, such as PD-L1, CD8-positive T cells, or major histocompatibility complex expression, as identified by immunohistochemistry and gene signature profiling, genetic alterations, such as RAS and NF1, with efficacy, PK, immunogenicity, or other biomarker endpoints
Exploratory Health Utility Objective:	

 Generate health status utility scores of patients treated with cobimetinib plus atezolizumab and with pembrolizumab for pharmacoeconomic modeling 	
 Health status utility score based on the EQ-5D-5L

ADA=anti-drug antibody; DCR=disease control rate; DOR=duration of response; EORTC=European Organisation for Research and Treatment of Cancer; EQ-5D-5L=European Quality of Life 5-Dimension, 5-Level questionnaire; IRC=independent review committee; OS=overall survival; NCI CTCAE v4.0=National Cancer Institute Common Terminology Criteria for Adverse Events, Version 4.0; PD-L1=programmed death–ligand 1; PFS=progression-free survival; PK=pharmacokinetic; QLQ-C30=Cancer Quality of Life–Core 30; QOL=quality of life; RECIST v1.1=Response Evaluation Criteria in Solid Tumors, Version 1.1.

Study Design

Description of Study

Study CO39722 is a Phase III, multicenter, open-label, randomized study designed to evaluate the efficacy, safety, and pharmacokinetics of cobimetinib plus atezolizumab compared with pembrolizumab in treatment-naïve patients with advanced *BRAF*^{V600} wild-type melanoma. The patient population includes patients with locally advanced and unresectable or metastatic melanoma. *BRAF*^{V600} wild-type status will be determined using local testing and enrollment based on local testing that will be subsequently confirmed with central testing after enrollment. Patients who are enrolled based on *BRAF*^{V600} wild-type status by local testing may continue in the study even in cases when central testing gives a different result. If local test results are not available for enrollment, *BRAF*^{V600} wild-type status will be determined by central testing. Programmed death–ligand 1 (PD-L1) status will be determined using central testing, with < 1% immune cells (IC), with IC0 defined as being PD-L1 negative versus IC1, IC2, IC3 defined as being PD-L1 positive.

The primary objective of the study is to evaluate the efficacy of cobimetinib plus atezolizumab compared with pembrolizumab in treatment-naïve patients with advanced *BRAF*^{V600} wild-type melanoma, as measured by primary endpoint of progression-free survival (PFS) assessed by independent review.

This study will be conducted globally and approximately 450 patients will be randomized in a 1:1 ratio to one of two treatment arms:

- Arm A: Patients will receive 60 mg of cobimetinib by mouth (PO) on a 21 days on, 7 days off (21/7) schedule (dosing on Days 1–21, followed by no dosing on Days 22–28) plus 840 mg of atezolizumab by intravenous (IV) infusion on Days 1 and 15 of each 28-day cycle (n=225).
- Arm B: Patients will receive 200 mg of pembrolizumab administered by IV infusion every 3 weeks (Q3W) (n=225).

Stratification factors are PD-L1 status (IC0 vs. IC1, 2, 3), baseline serum LDH level (less than or equal to the upper limit of normal [ULN] vs. greater than the ULN), and geographic region (North America vs. Europe vs. Australia, New Zealand, and others).

A permuted-block randomization will be applied to ensure a balanced assignment to each treatment arm. Randomization and stratification will be managed through an interactive Web-based response system (IWRS).

The Sponsor will monitor enrollment in each region (North America, Europe, Australia, New Zealand, and others). To ensure balanced global enrollment, the Sponsor may institute temporary limitations on enrollment in certain regions in the event of disproportionate accrual of patients.

Assessments and Monitoring

After signing informed consent, all patients will undergo screening procedures that include testing for *BRAF*^{V600} wild-type melanoma and PD-L1 status; laboratory tests (e.g., hematology, chemistries, liver function tests); left ventricular function evaluation (on echocardiogram [ECHO] or multiple-gated acquisition [MUGA] scan); ECG, contrast-enhanced computed tomography (CT) or magnetic resonance imaging (MRI) scans of the brain, chest, abdomen, and pelvis; and ophthalmologic assessments.

All eligible patients will be randomized to treatment in a 1:1 ratio to either Arm A (cobimetinib plus atezolizumab) or Arm B (pembrolizumab).

All patients will be closely monitored for safety and tolerability during all cycles of therapy, at the treatment discontinuation visit, and during the follow-up period. The National Cancer Institute Common Terminology Criteria for Adverse Events, Version 4.0 (NCI CTCAE v4.0) will be used to characterize the toxicity profile of study treatments for all patients. Patients will be assessed for adverse events according to the schedule of activities and as necessary throughout the study.

Tumor response will be evaluated according to Response Evaluation Criteria in Solid Tumors, Version 1.1 (RECIST v1.1). Any evaluable and measurable disease must be documented at screening and re-assessed at each subsequent tumor evaluation. Investigators will assess tumor response at 8-week intervals, regardless of any dose delays or treatment cycle.

Study treatment will continue for all patients until investigator-determined disease progression according to RECIST v1.1 that is confirmed by repeat scans 4–8 weeks later, unacceptable toxicity, death, patient or physician decision to withdraw, or pregnancy, whichever occurs first. Patients who experience disease progression must have scans repeated 4–8 weeks after initial documentation of progression to confirm disease progression. These results will be used as part of the exploratory analyses for assessing efficacy based on immune-modified RECIST. Tumor assessments are to continue according to schedule for patients who discontinue treatment for reasons other than confirmed disease progression. Clinically stable patients who have disease progression may continue, as described below.

Clinically stable patients who have a favorable benefit–risk ratio may continue study treatment following radiographic progression per RECIST v1.1 but approval will need to be provided by the Medical Monitor on a case-by-case basis. Patients who continue treatment beyond radiographic disease progression will be closely monitored. Treatment will be discontinued if clinical deterioration because of disease progression occurs at any time or if persistent disease growth is confirmed on follow-up scans performed 4–8 weeks later.

Patients who discontinue one study drug in Arm A may be able to continue the other study drug, per guidelines for management of specific adverse events. After treatment discontinuation,

patients will be followed for disease progression if applicable, and followed for survival until death, withdrawal of consent, or loss to follow-up, whichever occurs first. If a patient withdraws from the study, study staff may use a public information source (e.g., county records) to obtain information about survival status only.

This study will not allow crossover to other study drug(s) at the time of progression.

All patients who discontinue from study treatment because of radiographic disease progression or any other reasons will be asked to complete the European Quality of Life 5-Dimension, 5-Level questionnaire (EQ-5D-5L) and the European Organisation for Research and Treatment of Cancer Quality of Life Questionnaire—Core 30 (EORTC QLQ-C30), approximately every 28 days for 6 months after the last dose of study treatment.

Dosing of Study Treatment beyond Disease Progression

Dosing of study treatment beyond RECIST v1.1–defined disease progression is allowed for patients in all treatment arms.

Dosing of study treatment will continue until unacceptable toxicity or loss of clinical benefit, as determined by the investigator, after an integrated assessment of radiographic and biochemical data, local biopsy results (if available), and clinical status (e.g., symptomatic deterioration such as pain secondary to disease). Because of the possibility of an initial increase in tumor burden caused by IC infiltration in the setting of a T-cell response (termed pseudoprogression) with anti-PD-1 or anti-PD-L1 treatment, radiographic progression per RECIST v1.1 may not be indicative of true disease progression. In the absence of unacceptable toxicity, patients who meet criteria for disease progression per RECIST v1.1 while receiving study treatment will be permitted to continue study treatment if they meet all of the following criteria:

- Evidence of clinical benefit, as determined by the investigator following a review of all available data
- Absence of symptoms and signs (including laboratory values, such as new or worsening hypercalcemia) indicating unequivocal progression of disease
- No decline in Eastern Cooperative Oncology Group (ECOG) Performance Status that can be attributed to disease progression
- Absence of tumor progression at critical anatomical sites (e.g., leptomeningeal disease) that cannot be managed by protocol-allowed medical interventions
- Approval by the Medical Monitor

Safety Data Review

The Sponsor's study team will review data on adverse events, serious adverse events, the frequency of deaths from all causes, and any other safety data (for both treatment arms combined) in the study on an ongoing basis.

It is the responsibility of the study team to review accumulating safety data, to assess and monitor ongoing safety in patients, to evaluate potential changes to the clinical study protocol, and ultimately, to safeguard patient safety.

An independent Data Monitoring Committee (iDMC) will be employed to conduct periodic evaluations of safety data. All analyses for the iDMC's review will be prepared by an independent data coordinating center. Specific details, including responsibilities and structure of the iDMC, will be specified in an iDMC charter.

Number of Patients

The planned enrollment specifies a total of approximately 450 patients.

Target Population

